13.4.1 Site Qualification and Site Initiation Visit

The Site Qualification Visit enables SRS Medical to determine acceptability of site for subject population, expected enrollment, appropriate space for study equipment including limited access to investigational product and availability of an accredited clinical laboratory. These visits also determine the qualification and availability of investigator, sub-Investigators, and support staff, staff's previous clinical research experience, and the monitoring requirements. This visit will be documented in a site qualification report. This visit may be completed on site or remotely. Investigation site selection rationale can be based on prior experience of the sponsor with the principal investigator or the investigation site. Previously used sites may not require an addition qualification visit however justification for their use will be documented.

During the Site Initiation Visit (or Investigator Meeting), a review of the CIP, discussion of the Investigator's Brochure and discussions on the function/use of the system/equipment with the investigator/staff will occur. Should the PI choose to delegate study related tasks to qualified personnel under their direct supervision, this will be documented on the Delegation of Authority Log that will include names, initials, signatures, functions, and designated authorizations for the principal investigator and members of the investigation site team. In addition, delegated site personnel must be trained on the study relative to the tasks that have been assigned to them and this will be documented on the training log.

Before enrolling any subjects in this study, site personnel and the investigator will be trained on the protocol, the CRFs and instructions for their completion, the procedure for obtaining informed consent, and the procedure for reporting AEs, SAEs, SADEs and UADEs.

CONFIDENTIAL

13.4.2 Interim Monitoring Visits

Interim monitoring visits are made periodically per the monitoring plan to assess the investigator's adherence to the CIP, IRB requirements, maintenance of records and reports and review of source documents for accuracy, completeness, legibility, omissions and equipment calibration records. In cases where the site is not able to grant the monitor access to the electronic medical record, the investigational site staff will obtain copies of the electronic medical record and number the pages consecutively, sign and date the packet to indicate they are certified copies of the medical record. The monitors will acquire information to assess the progress of the study (toward meeting study objectives) and identify any concerns that stem from observation of device performance and/or review of the investigator's subject records, study management documents, regulatory documents, device tracking and verifying each subject has signed informed consent documents. Resolution of outstanding issues and completion of assigned tasks will be documented by the monitors. The Investigator agrees to accommodate and be available at monitoring visits conducted at a reasonable time in a reasonable manner, as needed.

13.4.3 Close Out Visit

The monitor will conduct a final Close-Out Visit at the sites for all sites. If investigational product remains at the site then a site visit is required to collect and document the return of any unused investigational products. A remote close out visit may occur at sites where investigational product has never been shipped or final device reconciliation has been completed at previous monitoring visits. Close out visits instruct the site on adherence to record retention requirements, ensure final data has been reconciled and a final monitoring report, to include the study status at the site, shall be prepared by the monitors (or designates).

Routine close-out activities shall be conducted to ensure that the principal investigator's records are complete, all documents needed for the sponsor's files are retrieved, remaining clinical investigation materials are retrieved or disposed of, previously identified issues have been resolved and all parties are notified including the EC and regulatory authorities, if required.

Ensure that:

- essential documents are complete and up to date,
- CRFs are completed,
- outstanding queries are resolved,
- the current status of all ongoing adverse events is documented,
- arrangements are made for archiving and record retention, and
- disposition of investigational devices and other clinical investigation materials is documented.

13.4.4 Site Audits

SRS Medical may choose to perform random audits throughout the study as part of implementing quality assurance. The purpose of this audit (which is independent of and separate from routine monitoring or quality control functions) is to evaluate study

CONFIDENTIAL

conduct and compliance with the protocol, applicable regulatory requirements, and study-specific procedures. The plan for this audit may be guided by the number of subjects at the site and any identified problems (such as non-compliance to the protocol). Non-compliance to the protocol and applicable regulatory requirements by the investigator/institution will lead to prompt action by SRS Medical to secure compliance. If the monitoring and/or auditing identify serious and or persistent non-compliance by the investigator/institution, SRS Medical may terminate the investigator/institution participation in the study.

14 STATISTICAL CONSIDERATIONS

This study is a multi-center, prospective, open-label, single-armed clinical study.

14.1 Level of Significance, Power and Sample Size

A hypothesis test that the proportion of successes in the treatment group is statistically significantly greater than 50% will be computed. In order to have an 80% chance of showing that the success proportion in the Spanner group is statistically significantly greater than 50%, assuming that the device can achieve a 65% success rate, with $\alpha=0.05$, a sample size of $n=85$ completers will be needed for the study. The sample size calculation was based on an exact binomial one sample test.

14.2 Expected Drop-out Rates

Assuming a dropout rate of 20%, the total sample size of $n=105$ subjects will be required for the study. A hypothesis test that the proportion of successes in the treatment group is statistically significantly greater than 50% will be computed.

14.3 Primary Effectiveness Variable and Pass/Fail Criteria

The primary effectiveness endpoint is the success/failure of the subject to have a successful urinary void at all four study visits: (a) upon initial placement of the first stent (Visit 1), and (b) at all three visits in which the subject has a stent placed for 30 days (Visits 2, 3 and 4).

The primary effectiveness endpoint will be marked as a failure for a subject if any of the following occur:

- PVR of >150 ml at any visit (Visits 1, 2, 3, and 4)
- The subject withdraws from the trial

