8.3 Study Hypotheses

8.3.1 Primary Endpoint: Assessment of PVR over 90 days

PVR levels will be monitored throughout the 90 days of stent use to confirm that the subject is able to successfully empty his bladder. PVR levels are assessed on Visits 1, 2, 3 and 4 while stent is in place using abdominal ultrasound. The hypothesis is that over 90 days of stent use, 50% of the subjects will be able to successfully empty their bladder, as defined by PVR of ≤ 150 ml at all four visits.

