14.11 Treatment of Missing Data, Including Lost to Follow-up and Withdrawals

For endpoint evaluations subjects with missing data due to missed visit, lost-to-follow-up or study withdrawal will have their missing data imputed using a multiple imputation method. Unless otherwise specifically noted, no statistical techniques will be used to impute missing values in other analyses of study data.

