4.2.1. Primary Effectiveness Endpoint

PVR levels will be monitored throughout the 90 days of stent use to confirm that the patient is able to successfully empty his bladder. PVR levels are assessed on Visits 1, 2, 3 and 4 while stent is in place using abdominal ultrasound. The hypothesis is that over 90 days of stent use, 50% of the patients will be able to successfully empty their bladder, as defined by PVR of ≤ 150 ml at all four visits.

Patients where the PVR is >150 ml at 1 or more of the 4 visits will be considered a *treatment failure*. Patients who fail to attend any of the 4 scheduled visits, or withdraw prematurely, will also be treated in primary the analysis as a *treatment failure*. Patients where the PVR is <150 ml at all 4 visits will be considered a *treatment success*.

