- Missing data may have an impact upon the interpretation of the trial data. The primary presentation of the results will be based on the observed data only. A sensitivity analysis (worst-case) will be performed by imputing the outcome for the primary and secondary endpoints as *failures* for the binary outcomes if the patient misses an evaluation visit or if the patient withdraws prematurely prior to attending the required visits. Section 14.11 of the protocol contains a discussion on the use of multiple imputation.
- Date variables will be formatted as DDMMYY for presentation.
- SAS® Version 9.2 or more recent, or a similar statistical package will be the statistical software package used for all data analyses.
- All data from this study will be presented in a listing. All listings will be sorted by patient number and visit date, as applicable.
- Table and listing numbering will follow ICH guidelines for post-text table and listing numbering.

Handling of Missing or Partial Dates for Adverse Events

If a portion of the start date of an adverse event is missing, or the entire date is missing, and the missing portion results in the treatment emergent determination being indeterminate, the adverse event will be considered *treatment emergent*.

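### No rule scores an attended visit without a PVR measured with the stent in place, and the three missing-data rules for the primary endpoint contradict one another

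*Protocol*

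**What the plan says.** **Endpoint.** Protocol 8.3.1 states that "PVR levels are assessed on Visits 1, 2, 3 and 4 while stent is in place using abdominal ultrasound", and SAP 4.2.1 repeats it. Protocol 14.3 asks for a successful void at Visit 1 and "at all three visits in which the subject has a stent placed for 30 days". The hypotheses in Protocol 14.6.3 and SAP 13.2 concern voiding while the Spanner is implanted.

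**Pass and fail rules.** Protocol 14.3 introduces its list with "The primary effectiveness endpoint will be marked as a failure for a subject if any of the following occur". The list has two entries: PVR above 150 ml at any visit, and withdrawal. SAP 4.2.1 adds a further class of failures: "Patients who fail to attend any of the 4 scheduled visits, or withdraw prematurely, will also be treated in primary the analysis as a". Its success sentence begins "Patients where the PVR is <150 ml at all 4 visits will be considered a". That sentence does not mention the stent.

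**Missing data.** SAP 8 says "The primary presentation of the results will be based on the observed data only". It makes failure imputation a worst-case sensitivity analysis that applies "if the patient misses an evaluation visit or if the patient withdraws prematurely prior to attending the required visits". Protocol 14.11 says that "subjects with missing data due to missed visit, lost-to-follow-up or study withdrawal will have their missing data imputed" by multiple imputation.

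**After stent loss.** Protocol 21.5 to 21.5.7 is offered as guidance. It has a subject continue and attend the next visit after removal for infection, bleeding, pain or meatal symptoms, and after migration, expulsion, retention or malfunction. If an adverse event is unresolved at that visit, no stent is placed. Withdrawal is directed in 21.5.8 for a PVR above 350 ml on two measurements.

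**Population.** The primary set is ITT: every enrolled subject with an attempted implant (Protocol 14.6.1).

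**The concern.** The protocol provides for a subject who remains enrolled and attends a visit without a stent. Visits 2 and 3 list the PVR before the next stent is placed, and Visit 4 places none. A stent lost between visits and not replaced therefore leaves an attended visit with a PVR taken without a stent, a PVR taken after re-placement at that visit, or no PVR.

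Such a subject has not withdrawn and has not missed a visit, and he may have no PVR above 150 ml, so no listed failure applies. If he has no valid PVR, the one general rule that reaches him is the observed-data rule in SAP 8, under which he can be left out. A failed insertion with no in-stent PVR at Visit 1 is in the same position unless the subject withdraws.

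In a single-arm trial tested against 50%, removing men who lost the device from the denominator raises the observed success rate. The claim at stake is that the stent can replace a catheter for 90 days.

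**Working it through.** **1. The plan's own figure.** Inputs from Protocol 14.1 and SAP 5.3: p0 = 0.50, p1 = 0.65, n = 85 completers, 20% dropout, N = 105. By normal approximation, power = Φ[(0.15 − z × 0.5/√85) / √(0.65 × 0.35/85)]. This gives 80.1% at one-sided 0.025 and 88.0% at one-sided 0.05, matching the stated 80% and 88%. The exact test that the documents name gives 73.6% (pass mark 53/85) and 86.0% (51/85), which is a separate matter. For dropout, 105 × 0.8 = 84.

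**2. The rules side by side.**

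| Rule | Missed visit or withdrawal | Attended, no in-stent PVR |
|---|---|---|
| Protocol 14.3 | withdrawal fails; missed visit not listed | not listed |
| SAP 4.2.1 | failure in the primary analysis | not listed as failure |
| SAP 8, primary presentation | observed data only | observed data only |
| SAP 8, worst case | failure, as sensitivity analysis | not listed |
| Protocol 14.11 | multiple imputation | not listed |

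The middle column holds three incompatible treatments. In the last column, only the observed-data rule applies.

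**3. Pass marks.** The pass mark is the smallest r with P(X ≥ r | n, 0.5) ≤ α, exact binomial. The protocol uses one-sided 0.025; the SAP's one-sided 95% bound corresponds to 0.05.

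| n | α = 0.025 | α = 0.05 |
|---|---|---|
| 105 | 64 (p = 0.0157; 63 gives 0.0252) | 62 (p = 0.0392; 61 gives 0.0590) |
| 100 | 61 (p = 0.0176; 60 gives 0.0284) | 59 (p = 0.0443; 58 gives 0.0666) |

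Assume five subjects without an in-stent PVR at some attended visit (not a figure from the documents). Scored as failures they leave n = 105; dropped, n = 100. The verdict then differs for 61 to 63 in-stent successes at 0.025 and for 59 to 61 at 0.05. For example, 61/105 gives p = 0.0590 and 61/100 gives p = 0.0176. The count 61 is the only one at which failure scoring misses at both levels and dropping passes at both, so it is the most striking case, not a typical one.

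**4. How often this would matter.** If the other 100 succeed at 65%, X ~ Bin(100, 0.65):
- at 0.025, P(X ≥ 61) − P(X ≥ 64) = 0.8276 − 0.6269 = 0.2007
- at 0.05, P(X ≥ 59) − P(X ≥ 62) = 0.9123 − 0.7699 = 0.1424

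With one such subject, X ~ Bin(104, 0.65), the chance of passing at 0.025 is 80.1% if he fails and 85.3% if he is dropped.

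**5. False-positive side.** Suppose true in-stent success over all 105 is exactly 50%, counting k stent-loss subjects as failures. Dropping them raises the rate to 0.5 × 105/(105 − k), which is 0.525 for k = 5. The chance of passing at nominal 0.025 is 1.6% under failure scoring. Under dropping it is 3.7% (k = 3), 5.4% (k = 5), 15.1% (k = 10) and 50.4% (k = 20).

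**6. Cost of failure scoring in power.** If the planned 65% already counts stent loss as failure, power is P(X ≥ 64 | 105, 0.65) = 83.5% at 0.025. If five failures come on top, it is P(X ≥ 64 | 100, 0.65) = 62.7%.

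Steps 3 to 6 ignore dropout. The same conflict affects the planned dropouts: removing 21 of 105 gives 76.3% power (pass mark 52/84), while scoring them as failures gives P(X ≥ 64 | 84, 0.65) = 1.9%, both at 0.025. That is a separate matter from stent loss.

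**The case against.** A reader might infer that a man without the device can be counted as a device success, because neither the failure lists nor the SAP success sentence mentions the stent. The documents do not support that as a fair reading. Protocol 8.3.1, 14.3 and 14.6.3 and SAP 4.2.1 and 13.2 all tie the endpoint to a stent in place, and Protocol 14.3 does not say that its failure list is exhaustive. It remains a remote literal reading.

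A stronger defence is that SAP success needs a qualifying PVR at all four visits and the primary result is reported on ITT, so a subject without one simply does not succeed. That is a sensible reading, and it is the one that should be written down. It does not settle the matter, because SAP 8 states a different basis for the primary presentation and gives failure imputation only the status of a sensitivity analysis.

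Nor is a visit without a stent inevitable after removal. Section 21.5 is guidance, 21.3 allows replacement, and a subject may withdraw and so fail. A new stent placed at the visit could be followed by a PVR, as at Visit 1. This narrows the number of cases but raises another unanswered question: whether a PVR through a newly placed stent meets a condition written for one worn 30 days.

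A reader might also infer that the scoring will be chosen once the open-label results are known. The documents do not support that. Protocol 14.7 requires the SAP to be signed before the first enrolment, and 14.10 requires deviations to be described and justified, if required.

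**Conclusion.** The point holds and should be fixed. The conflict between SAP 4.2.1, SAP 8 and Protocol 14.11 is explicit. The attended visit without an in-stent PVR, and the attempted implant without one at Visit 1, have no scoring sentence. The direction is clear: dropping such subjects favours the device compared with failing them.

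The size is uncertain because it rests on an assumed number of stent-loss subjects. With five of 105, the choice matters in a band of three success counts at either significance level. With one subject it moves the chance of passing by about five percentage points (85.3% − 80.1% = 5.2). The larger effects in step 5 require ten or more such subjects.

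**What to change.** 1. In Protocol 14.3 and SAP 4.2.1 to 4.2.2, state that success requires a PVR at or below the threshold, measured with a stent in place, at every required visit (Visits 1 to 4, or Visits 1 and 2 for the 30-day endpoints). State that any other ITT subject is a non-success, including attempted implants with no PVR at Visit 1.
2. State whether a PVR taken after stent replacement, between visits or at the same visit, qualifies.
3. Amend SAP 8 and Protocol 14.11 so that observed-only and multiple-imputation results are sensitivity analyses.
4. Report removals unrelated to device failure separately, for example removal before an MRI (Protocol 7.5). Scoring these as non-success is a choice of estimand and should be stated as one.
5. In the SAP 4.2.1 success sentence, change <150 ml to ≤150 ml. As written, exactly 150 ml is neither success nor failure, although the same section defines the endpoint as ≤150 ml.
6. Confirm that the case report forms and table templates carry stent status at each PVR. Their fields are not in the documents.

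The cost is wording in two documents, a programming flag and the forms check. Protocol 16 may require an FDA supplement. The observed success rate may be lower: step 6 gives 83.5% or 62.7% power before dropout, depending on whether the planned 65% already allows for stent loss. The protocol should say which it assumes.

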8 OBJECTIVES AND HYPOTHESES OF THE CLINICAL INVESTIGATION

8.1 Primary Objective

The primary objective of the clinical study is:

- To determine the proportion of subjects who achieve adequate bladder drainage over 90 days, defined as a post-void residual (PVR) of ≤ 150 ml.
- The pre-specified success criterion for this study is that ≥ 50 percent of subjects will achieve adequate bladder drainage over 90 days.

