12.1.6 Unscheduled Visits

If the subject returns to a medical facility due to a BPH or stent related issue, then complete an Unscheduled Visit eCRF.

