21.2 AE Assessment, Documentation and Reporting

Complete an Adverse Event eCRF. Provide a complete description of the nature, severity and circumstances of the Adverse Event including results of physical examinations, diagnostic tests, treatments given, outcome of treatments and the subject's final condition.

Reports to the Sponsor.

Report all Serious Adverse Events, and Unanticipated Adverse Device Events to the Sponsor as soon as adequate information about the adverse event is available, but no later than 5 working days from the date the Investigator first became aware of the event. Notify the Sponsor by completing, or partially completing, Adverse Event eCRF.

Reports to the IRB.

Investigators are required to report all Unanticipated Adverse Device Events (See 21.3 for definition) to the reviewing IRB no later than 10 working days from the date that the Investigator first became aware of the event. In addition, the Investigator must comply with any other reporting requirements of the reviewing IRB.

21.3 Reporting Device Deficiencies.

If a device deficiency is suspected, The Spanner should be evaluated to determine if removal or replacement is necessary. All device deficiencies related to the identity, quality, durability, reliability, safety or performance of an investigational medical device shall be documented throughout the clinical investigation and appropriately managed by the sponsor. All Device Deficiencies, whether resulting in a symptom or not, should be reported as an Adverse Event and an Adverse Event eCRF should be completed.

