21.5.6 Migration or Expulsion of the Device

Migration- If migration of the Spanner is suspected, perform an x-ray or cystoscopy, if possible, to document the location of the device prior to attempting removal.

Subsequently, the device should be removed, either by locating and grasping the retrieval suture to remove the device or, if the retrieval suture cannot be located, by retrieving the device cystoscopically. In either case, care should be taken to assure that the proximal balloon is deflated prior to withdrawing the device through the urethra and that all of the device components are removed. (If possible, the balloon may be deflated by cystoscopically locating the suture that is attached to the proximal balloon and pulling it to remove the balloon drain plug to allow the balloon to empty. Alternately, the balloon may be ruptured cystoscopically using a cautery tool or wire guide.)

Record a Device Deficiency eCRF and return the device to the Sponsor. Provide a detailed description of any damage to the device that is known to have occurred as a result of removing the device (i.e. balloon punctured, suture between stent and distal anchor cut).

The subject should continue in the study and attend the next study visit.

Expulsion - Record a Device Deficiency eCRF and return the device to the Sponsor. Provide a detailed description of any damage to the device that is known to have occurred as a result of removing the device (i.e. balloon punctured, suture between stent and distal anchor cut). The subject should continue in the study and attend the next study visit.

Urinary Retention- If urinary retention occurs, and there is a question of whether the retention is related to bladder performance, an urodynamic evaluation should be considered to determine if bladder performance is contributing to urinary retention.

For urinary retention in a subject, cystoscopy or an x-ray should be performed prior to removal of The Spanner to verify whether device migration or inadequate stenting is the cause of the urinary retention. Subsequently, the device should be removed. After Spanner removal, the subject should be evaluated to determine voiding capability and urinary catheter bladder drainage instituted if needed.

An Adverse Event should be recorded and the device returned to the Sponsor. The subject should continue in the study and attend the next study visit.

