13.2. Primary Effectiveness Endpoint Analysis

The results of the Primary Effectiveness Endpoint analysis will be presented in the SRS TLF, Table 31.

The primary effectiveness endpoint for this study is the proportion of patients who achieve adequate bladder drainage over 90 days, defined as a post-void residual (PVR) of ≤ 150 ml. The pre-specified success criterion for this study is that ≥ 50 percent of patients will achieve adequate bladder drainage at each of the 4 evaluations over 90 days. The primary objective will be met if the one-sided lower bound of the 95% confidence limit for the incidence of patients who achieve adequate bladder drainage at each of the 4 evaluations over 90 days is $\geq 50\%$. The null and alternative hypotheses are as follows:

$$H_0: \pi \leq 0.5$$

$$H_a: \pi > 0.5$$

π is the proportion of patients with maintenance of successful voiding during the Spanner implantation period.

Results based on the ITT population will be presented in Table 32 entitled *Primary Effectiveness Endpoint Analysis* (PVR of ≤ 150 ml) (ITT population). The table will contain the point estimate and the confidence limit based on patients who met the primary endpoint.

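### A man with retention, catheter drainage or an unplanned stent removal or replacement between visits can still count as a primary success, because only scheduled readings, withdrawal and missed visits are scored

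*Protocol*

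**What the plan says.** **What is claimed.** The primary objective is "To determine the proportion of subjects who achieve adequate bladder drainage over 90 days, defined as a post-void residual (PVR) of ≤ 150 ml" (Protocol 8.1). Protocol 8.3.1 makes this operational: success is "as defined by PVR of ≤ 150 ml at all four visits", measured with the stent in place. SAP 13.2 says of the tested parameter that "π is the proportion of patients with maintenance of successful voiding during the Spanner implantation period"; Protocol 14.6.3 describes it in the same way.

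**What is scored as failure.**
- Protocol 14.3: "PVR of >150 ml at any visit (Visits 1, 2, 3, and 4", or withdrawal from the trial.
- SAP 4.2.1: the same, plus failure to attend any scheduled visit.
- Protocol 21.5.8: PVR above 350 ml on two measurements within a few hours, at a scheduled or any other medical visit, leads to withdrawal. By 14.3 that is a failure.

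**What happens between visits.**
- Device deficiency (Protocol 21.3): "If a device deficiency is suspected, The Spanner should be evaluated to determine if removal or replacement is necessary".
- Retention (Protocol 21.5.6): the stent comes out. "After Spanner removal, the subject should be evaluated to determine voiding capability and urinary catheter bladder drainage instituted if needed". The man stays in the study and attends his next visit.
- Migration, expulsion, occlusion or malfunction (21.5.6 and 21.5.7): he likewise stays in the study.
- At the next scheduled visit (21.5), a man with no unresolved adverse event gets a new stent and resumes the schedule.
- Unscheduled care (Protocol 12.1.6): "If the subject returns to a medical facility due to a BPH or stent related issue, then complete an Unscheduled Visit eCRF". Nothing links that form to the endpoint.

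**The concern.** The parameter is described as voiding maintained over the whole implantation period, but the scoring looks at four appointments about 30 days apart. Protocol 7.2 and 7.3 list retention (with migration, with clotting or with neither), migration and expulsion as anticipated. A man may therefore have his drainage fail, go back to a catheter for a time, be re-stented, and meet no failure criterion.

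The trial is single-arm against a fixed 50%, and the stent is offered as an alternative to a catheter. Men of this kind can only push the success proportion up, and no control arm carries the same error to offset it. The separate tables for adverse events, device deficiencies and stent removals do not show how many primary successes had such an event.

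**Working it through.** **1. Which events reach the endpoint**

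| Event between visits | Status in the study | Scored as primary failure? |
|---|---|---|
| PVR >350 ml on two measurements, any medical visit | Withdrawn (21.5.8) | Yes, through withdrawal |
| Retention, stent removed, catheter if needed | Continues (21.5.6) | No rule |
| Migration, expulsion, occlusion, malfunction | Continues (21.5.6, 21.5.7) | No rule |
| Stent replaced for a suspected deficiency | Possible under 21.3 | No rule |
| Unscheduled PVR of 151–350 ml | Continues | No rule |
| Next scheduled visit missed | Not a withdrawal in itself | SAP 4.2.1 only |

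Two routes to being counted as a success follow.
- *Replacement before the next visit.* The new stent is in place and the scheduled reading is at most 150 ml.
- *No stent at the next visit.* The man attends, so he is neither missed nor withdrawn, and no PVR above 150 ml is recorded. How that visit is scored is not stated. SAP section 8 bases the primary presentation on observed data, SAP 4.2.1 treats missed visits as failures, and Protocol 14.11 uses multiple imputation.

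Protocol 21.5.6 (retention: continue) and 21.5.8 (PVR >350 ml twice: withdraw) can both apply to one man. His primary outcome then depends on which passage the site follows.

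**2. The plan's own figure**

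Inputs: null 50%, assumed 65%, 80% power, two-sided 5% (Protocol 14.1, SAP 5.3).

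n = ((1.960 × √(0.5 × 0.5) + 0.842 × √(0.65 × 0.35)) / 0.15)² = 84.8, rounded up to 85, as stated. This is the normal approximation. The exact binomial test that the plan names gives 73.6% power at n = 85 and one-sided 0.025 (53 successes needed). That is a separate matter.

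**3. Pass marks at N = 105, exact binomial, null 50%**
- One-sided 0.025 (Protocol 14.6.3): 64 successes, P = 0.0157; 63 would give 0.0252.
- One-sided 95% bound (SAP 13.2): 62 successes, P = 0.0392; 61 would give 0.0590.

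**4. Illustration of size**

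Let d be the share of all men who have such an event and still pass. The documents give no value, so the range is assumed. Recorded success = event-free success + d. Take event-free success as exactly 50%, so that any declared success is false with respect to maintained voiding.

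| d | Men of 105 | Share of 15-point planning margin | Recorded rate | Chance of ≥64 | Chance of ≥62 |
|---|---|---|---|---|---|
| 0 | 0 | 0 | 50% | 1.6% | 3.9% |
| 3 points | 3.15, about 3 | 3/15 = 0.20 | 53% | 6.2% | 12.6% |
| 5 points | 5.25, about 5 | 5/15 = 0.33 | 55% | 12.9% | 23.2% |
| 10 points | 10.5, about 11 | 10/15 = 0.67 | 60% | 46.3% | 62.0% |

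**5. A tipping point that needs no assumed event rate**

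At the planned 65%, 0.65 × 105 = 68.25, so about 68 recorded successes. Rescoring 68 − 64 + 1 = 5 men as failures would take the count below the protocol's pass mark. Rescoring 68 − 62 + 1 = 7 would take it below the SAP's.

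**The case against.** The case on the other side is substantial.

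- *The 90-day period is defined.* Protocol 8.3.1 and SAP 13.2 tie it to all four evaluations. This stands. A reader might infer that the endpoint is undefined or that the four-visit rule is an error; the text supports neither.
- *Very high residuals do fail.* A reader might infer that any man with a high PVR between visits is a success. That is wrong for PVR above 350 ml on two measurements, which means withdrawal.
- *Early replacement rests on one general phrase in 21.3.* The specific sections on migration, occlusion and retention remove the stent and send the man to his next visit, where 21.5 allows a new one. At Visits 2 to 4 PVR is taken before that stent goes in, so most such men would arrive without one. This stands as a limit on the first route. It does not close the gap, because a man who attends without a stent meets no failure criterion either. Protocol 14.3 describes Visits 2 to 4 as following 30 days of stent placement, but that condition is not in its failure list.
- *Failing a man on one unscheduled PVR above 150 ml would be too strict.* This stands. Attachment B allows two attempts at scheduled visits, unscheduled visits do not require a PVR, and the result would depend on who happens to return.
- *The events are reported in safety and device tables.* True, but no described analysis crosses them with primary success.
- *The 3 to 10 point range has no source.* True; it is illustration only.

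**Conclusion.** The point holds in a limited form. The four-visit endpoint is clearly defined and can stay. It does not by itself support a statement that voiding was maintained through the implantation period, because retention, return to catheter drainage, and unplanned stent removal or replacement between visits are not scored and the men stay in the study. They can count as successes; the documents do not show that they always would.

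The direction of any bias is upward. Its size is unknown. The error rates shown hold only under the assumed shares, an event-free rate of exactly 50%, and all 105 men entering the analysis. A reader might take them as an estimate of inflated false-positive risk in this trial; without an event rate they are not. The tipping point of five to seven men at the planned success rate shows that a small number of such men could matter to the conclusion.

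**What to change.** 1. Leave the primary endpoint and its test unchanged.
2. Add to SAP 13.2 one prespecified supportive analysis in the ITT population. Success requires the primary criterion and, between visits, no retention event, no return to catheter drainage, and no unscheduled stent removal or replacement for occlusion, migration, expulsion or malfunction. Take these from the Adverse Event, Unscheduled Visit and Device Deficiency eCRFs.
3. Report unscheduled PVR readings of 151–350 ml among primary successes descriptively, not as automatic failures.
4. State how a scheduled visit attended without a stent is scored.
5. Word the primary conclusion as applying at the four scheduled visits unless the supportive analysis agrees.
6. Reconcile Protocol 21.5.6 and 21.5.8 for a man to whom both apply, so that his endpoint status does not depend on the site.

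The analysis costs one SAP paragraph and one table from forms already planned in Attachment E. The scoring rule and the reconciliation need short text edits. The downside is that the supportive rate can only equal or fall below the headline rate.
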